6.6.3 Adverse Events

The incidence and severity of adverse events is a primary endpoint in Monotherapy Expansion, along with the incidence and severity of DLTs during Cycle 1 for Monotherapy Dose Escalation and Combination Dose Escalation. The incidence and severity of adverse events is also a secondary endpoint for all cohorts.

Adverse events will be collected and coded using version 25.0 or later of the Medical Dictionary for Regulatory Activities (MedDRA) with descriptions by System Organ Class (SOC), High Level Group Term, High-Level Term, Preferred Term, and Lower-Level Term. Analysis of adverse events will be carried out on the Safety Analysis Set.

All AEs will be listed. The focus of AE summary will be on treatment-emergent AEs (TEAE). A TEAE is defined as an AE that occurs or worsens in the period from the first dose of study drug to 30 days after the last dose of study drug.

The severity of AEs will be graded by the Investigator according to the NCI CTCAE, version 4.03. The relationship of the AE to any study drug will be categorized as related or unrelated.

A subject who reports multiple TEAEs within the same Preferred Term (or SOC) is counted only once for that Preferred Term (or SOC) using the worst severity grade.

The TEAEs will be summarized by study part and dose level. Summary tables will be presented to show the number of subjects reporting TEAEs by severity grade and corresponding percentages. AE descriptions will be presented by decreasing frequency for a given SOC and Preferred Term. Separate listings and summaries will be prepared for the following types of TEAEs:

- All TEAEs
- DLTs (Monotherapy Dose Escalation and Combination Dose Escalation) (listing only)

- TEAEs by Grade/Severity
- Study-drug-related TEAEs – for the Phase 1 Combination, these TEAEs will be summarized based on relationship to any study drug, as well separately for ZN-c5 and Palbociclib
- TEAEs that are Grade ≥ 3 in severity
- TEAEs leading to study drug interruption and/or dose modification – for the Phase 1 Combination, these TEAEs will be summarized based on interruption and/or dose modification for any study drug, as well separately for ZN-c5 and Palbociclib
- TEAEs leading to study drug discontinuation – for the Phase 1 Combination, these TEAEs will be summarized based on discontinuation of any study drug, as well separately for ZN-c5 and Palbociclib
- TEAEs with outcome of death (fatal TEAEs)
- Serious TEAEs

Missing Grade:

Missing grades will not be imputed. AEs with missing grade will be reported as 'No Grade'. AEs with missing grade will be counted in "All Grades", but will not be counted in "Grade 3 or higher" columns.

Missing Relationship to Study Drug

An AE with a missing relationship to study drug will be categorized as 'Not determined' and will be included in summaries of related AEs. Imputed values will not be listed in data listings.

Adverse Events with Incomplete Dates

Imputation of dates for adverse events with incomplete dates will be performed only for determination of treatment emergence. Imputed dates will not be presented in data listings. The following algorithm will be used to estimate adverse event start dates for which only partial information is known:

- Missing day and month
 - If the year is same as the year of first day on drug, then the day and month of the start date of drug will be assigned to the missing fields.
 - If the year is prior to the year of first day on drug, then December 31 will be assigned to the missing fields.
 - If the year is after the year of first day on drug, then January 1 will be assigned to the missing fields.
- Missing month only
 - Treat day as missing and replace both month and day according to the above procedure.
- Missing day only
 - If the month and year are same as the year and month of first day on drug, then the start date of drug will be assigned to the missing day.

- If the month and year are before the year and month of first day on drug, then the last day of the month will be assigned to the missing day.
- If the month and year are after the year and month of first day on drug, then the first day of the month will be assigned to the missing day.

If the AE stop date is complete and the imputed start date as above is after the stop date, the start date will be imputed using the stop date.

Adverse events with partially missing stop dates will be imputed a stop date as follows:

- Year is missing – date left missing.
- Month is missing:
 - If year = year of data extract, impute as month of data extract;
 - Else, impute 'December'.
- Day is missing:
 - If year and month = year and month of data extract, impute as day of data extract;
 - Else impute 'last day of that month'.

6.6.3.1 Deaths

Summaries of deaths within 30 days of last dose of study medication (including cause of death) as well as a count of those occurring more than 30 days after last dose will be provided. All deaths reported will also be presented in a listing.

6.6.4 Laboratory Data

Laboratory assessments include:

Table 4 Laboratory Tests

Category	Parameters
Hematology	Hemoglobin, hematocrit, platelet count, WBC count with differential (neutrophils, eosinophils, basophils, lymphocytes, monocytes)
Coagulation	PT/INR, aPTT
Serum Chemistry	Total protein, albumin, BUN, creatinine, calculated CrCl, total bilirubin with direct bilirubin as applicable, AST (SGOT), ALT (SGPT), alkaline phosphatase, GGT, glucose, sodium, potassium, chloride, calcium, magnesium, phosphate, full lipid panel
Urinalysis	visual inspection, microscopic examination, and dipstick test for pH, protein, glucose, WBC, bilirubin, and blood
Pregnancy Test	β-hCG (for women of childbearing potential) During Screening, a serum pregnancy test must be performed. During the study, urine or serum pregnancy tests can be performed.

ALT = alanine aminotransferase; aPTT = activated partial thromboplastin time; AST = aspartate aminotransferase; β -hCG = beta-human chorionic gonadotropin; BUN = blood urea nitrogen; CPK = creatine phosphokinase; CrCl = creatinine clearance; GGT = gamma-glutamyl-transferase; PT/INR = Prothrombin Time – International Normalized Ratio; SGOT = serum glutamic-oxaloacetic transaminase; SGPT = serum glutamic pyruvic transaminase; WBC = white blood cell

A full lipid panel, regardless of fasting status, will be performed on C1D1, C3D1 (coinciding with the first on-study tumor assessment after 8 weeks) and C7D1 (6 months into the study). This will not be assessed in the Monotherapy Phase 2 part of the study.

In addition: Plasma 4 β -hydroxycholesterol and cholesterol will be analyzed (from the same blood draw as for PK) at the following time points of the Monotherapy Dose Escalation and Expansion cohorts:

[Cycle 1 Day 1] pre-dose (0 hr)

[Cycle 1 Day 15] pre-dose (0 hr)

[Cycles 2, 3 and 4 Day 1] pre-dose (0 hour)

All laboratory data will be stored in the database with the units in which they are originally reported. Laboratory data in summary tables and subject data listings will be presented in the International System of Units (SI units; Système International d’Unités).

Hematology, serum chemistry and coagulation tests will be programmatically graded according to NCI-CTCAE v4.03 toxicity grading as detailed in [Appendix 1 NCI-CTCAE V4.03 Toxicity Grading](#) when applicable. For parameters for which a CTCAE scale does not exist, reference ranges from the local laboratory will be used to determine programmatically if a laboratory parameter is below, within or above the normal range for the subject’s age, sex, etc.

Treatment-emergent laboratory abnormalities will be identified and will be the focus of laboratory data summarization. A treatment-emergent laboratory abnormality is defined as an abnormality that, compared to baseline, worsens by ≥ 1 grade in the period from the first dose of study drug to 30 days after the last dose of study drug. If baseline data are missing, then any graded abnormality (i.e., an abnormality that is Grade ≥ 1 in severity) will be considered treatment-emergent.

For laboratory results entered with inequality symbols ($<$, \leq , $>$, \geq), numeric values will be imputed by ignoring the inequality symbol(s) (e.g. “ <1.71 ” will be imputed as 1.71 for numeric analyses). Imputed values will not be listed in data listings.

For each laboratory test, Baseline and worst (maximum) CTCAE grade post-Baseline will be identified for each subject. For parameters for which a CTCAE scale does not exist, the Baseline and worst post-Baseline value will be identified as being below, within or above the normal range as detailed above. Change from Baseline will be calculated for all post-Baseline results.

Subjects will be characterized only once for a given assay, based on the worst severity grade observed during a period of interest (e.g., during the study or from Baseline to a particular visit).

Hematology, coagulation and serum chemistry data, and changes from Baseline will be summarized by dose level, by visit for visits from Baseline to C2D1 as well as EOT. Urinalysis and pregnancy test results will be listed only. Plasma 4 β -hydroxycholesterol and cholesterol will be listed only.

Shift tables for hematology, coagulation and serum chemistry will also be presented by showing change in CTCAE severity grade from Baseline to worst grade post-Baseline. A shift table for hematology showing change in CTCAE severity grade from Baseline to worst Cycle 1 value will also be presented.

For parameters for which a CTCAE scale does not exist, shift tables will be presented showing change in results from Baseline to worst post-Baseline category (below, within, or above normal range).

Separate listings and summaries may be prepared for laboratory abnormalities that are Grade ≥ 3 in severity.

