7.2 PARTICIPANT DISCONTINUATION/WITHDRAWAL FROM TREATMENT AND FROM THE STUDY

Subjects may be discontinued from the investigational treatment in the following situations:

- Documented progression of disease or clinical progression
- Death
- Investigator discretion
- Non-compliance with study drug or protocol
- Important protocol deviation
- Pregnancy
- Patient discretion
- Withdrawal of consent (subjects are free to withdraw participation at any time)
- Lost to follow-up
- Subjects incorrectly initiated on study treatment
- Intercurrent illness that would, in the judgment of the investigator, affect assessments of clinical status to a significant degree
- Unacceptable toxicity
- Liver testing abnormalities meeting Hy's Law criteria (See Section 10.4.7)
- Study termination by the Sponsor

Subjects who are withdrawn from the study but are evaluable will not be replaced. Any subject who is withdrawn and is not evaluable may be replaced to ensure a minimum number of evaluable patients.

Subjects may withdraw from any aspect of the voluntary exploratory research at any time, without prejudice to further treatment and independent of any decision concerning participation in other aspects of the study.

If there is strong evidence of clinical benefit and reasons to justify continuation of the study drug, even though treatment discontinuation criteria have been met, this decision must be reviewed with the Sponsor, and continuation of therapy may be allowed assuming all other treatment resumption criteria have been met.

Subjects will be discontinued from the study in the following situations:

- Death
- Lost to follow-up
- Withdrawal of consent
- Study end per protocol
- Early study termination by Sponsor

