8.4 DOSE-LIMITING TOXICITIES AND TOXICITY MANAGEMENT

8.4.1 DEFINITION OF DOSE-LIMITING TOXICITY MONOTHERAPY DOSE ESCALATION

A dose-limiting toxicity (DLT) is a toxicity as defined below, excluding toxicities clearly related to disease progression or intercurrent illness, which occurs during the DLT evaluation period (Cycle 1) in each cohort:

- Grade ≥ 3 hematologic toxicity present for more than 7 days
- Grade ≥ 3 neutropenia (ANC < 1000/mm³) with fever (a single temperature of > 38.3°C or a sustained temperature of ≥ 38°C for more than one hour)
- Grade 3 thrombocytopenia with bleeding
- Grade ≥ 3 or higher non-hematologic toxicity, except:
 - Grade 3 nausea or emesis with maximum duration of 48 hours on adequate medical therapy
 - Grade 3 diarrhea which persists for < 72 hours in the absence of maximal medical therapy
- Grade ≥ 2 non-hematologic treatment-emergent adverse event (TEAE) that in the opinion of the
 investigator is of potential clinical significance such that further dose escalation would expose
 subjects to unacceptable risk
- Treatment interruption of ≥ 4 days due to drug-related toxicity
- Liver enzyme and bilirubin abnormalities meeting Hy's Law criteria (See Section 10.4.7)
- Any death not clearly due to the underlying disease or extraneous cause

For certain toxicities, such as laboratory assessments without a clear clinical correlate, a discussion between the investigator and Medical Monitor may take place to determine if this adverse event (AE) should be assessed as a DLT necessitating dose reduction. In addition, any toxicity which occurs during the DLT evaluation period meeting the protocol-defined stopping criteria (Section 7.1) will be considered a DLT.

During the DLT evaluation period (Cycle 1), subjects not completing at least 24 days of scheduled daily dosing of ZN-c5 for reasons other than drug-related toxicity (e.g., withdrawal of consent, rapid disease progression, etc.) may be replaced based on the discretion of the Safety Review Committee.

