8.4.2 DEFINITION OF DOSE-LIMITING TOXICITY – COMBINATION DOSE ESCALATION

A DLT is a toxicity as defined below, excluding toxicities clearly related to disease progression or intercurrent illness, which occurs during the DLT evaluation period (Cycle 1) in each cohort:

- Hematologic:
 - o Grade 4 neutropenia
 - Febrile neutropenia (defined as neutropenia Grade ≥ 3 [ANC < 1000 cells/mm³] and a body temperature ≥ 38.5°C) requiring antibiotic or antifungal treatment
 - o Any Grade 4 thrombocytopenia (< 25,000/mm³ or <25.0 x 109/L)
- Nonhematologic:
 - o Grade ≥ 3 toxicities despite adequate treatment (e.g., nausea, vomiting, diarrhea)
- Other:
 - o Any palbociclib treatment delay of greater than 7 days to start Cycle 2

Subjects who do not receive at least 24/28 doses of ZN-c5 and/or at least 85% of palbociclib doses in Cycle 1 for reasons other than DLT will be replaced.

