10.4.7 HY'S LAW DEFINITION

(Excerpted/adapted from: https://www.fda.gov/media/116737/download)

Hy's Law is essentially a translation of Zimmerman's observation that pure hepatocellular injury sufficient to cause hyperbilirubinemia is an ominous indicator of the potential for a drug to cause serious liver injury. Thus, a finding of ALT elevation, usually substantial, seen concurrently with bilirubin > 2×ULN, identifies a drug likely to cause severe drug-induced liver injury (DILI) (fatal or requiring transplant) at a rate roughly 1/10 the rate of Hy's Law cases. It is critical to rule out other causes of injury (e.g., other drugs or viral hepatitis) and to rule out an obstructive basis for the elevated bilirubin, so that alkaline phosphatase (ALP) should not be substantially elevated. In all cases to date, the small number of Hy's Law cases has arisen on a background of an increased incidence of more modest signs of hepatocellular injury (e.g., greater incidence of 3 × ULN elevations in AT than seen in a control group).

Briefly, Hy's Law cases have the following three components:

- 1. The drug causes hepatocellular injury, generally shown by a higher incidence of **3-fold (3 ×) or greater elevations above the upper limit of normal (ULN) of ALT or AST** than the (non-hepatotoxic) control drug or placebo
- 2. Among trial subjects showing such aminotransferase (AT) elevations, often with ATs much greater than 3xULN, one or more **also show elevation of serum total bilirubin (TBL) to > 2 × ULN**, without initial findings of cholestasis (elevated serum ALP)
- 3. No other reason can be found to explain the combination of increased AT and TBL, such as viral hepatitis A, B, or C; preexisting or acute liver disease; or another drug capable of causing the observed injury

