11. APPENDIX 1 NCI-CTCAE V4.03 TOXICITY GRADING

11.1 Panel: Chemistry

Lab Test	Unit	Grade 1	Grade 2	Grade 3	Grade 4
Albumin, serum- low (hypoalbuminemia)	g/L	[30, LLN)	[20, 30)	<20	life-threatening consequences; urgent intervention indicated
Alkaline phosphatase (ALK) increased	U/L	(ULN, 2.5*ULN]	(2.5*ULN, 5*ULN]	(5*ULN, 20*ULN]	>20*ULN
Alanine aminotransferase (ALT) increased	U/L	(ULN, 3.0*ULN]	(3.0*ULN, 5.0*ULN]	(5*ULN, 20*ULN];	>20*ULN
Aspartate aminotransferase (AST) increased	U/L	(ULN, 3.0*ULN]	(3.0*ULN, 5.0*ULN]	(5*ULN, 20*ULN];	>20*ULN
Bilirubin increased	µmol/L	(ULN, 1.5*ULN]	(1.5*ULN, 3*ULN]	(3*ULN, 10*ULN]	>10*ULN
Calcium high (hypercalcemia)	mmol/L	(ULN, 2.9]	(2.9, 3.1]	(3.1, 3.4]; hospitalization indicated	>3.4; life-threatening consequences
Calcium low (hypocalcemia)	mmol/L	[2.0, LLN)	[1.75, 2.0)	[1.5, 1.75); hospitalization indicated	[0, 1.5); life threatening consequences
Creatine phosphokinase (CPK) increased	U/L	(ULN, 2.5*ULN]	(2.5*ULN, 5*ULN]	(5*ULN, 10*ULN]	>10*ULN
Creatinine increased	µmol/L	(1 – 1.5*baseline]; (ULN, 1.5*ULN]	(1.5 – 3.0* baseline]; (1.5*ULN, 3*ULN]	>3.0*baseline; (3*ULN, 6*ULN]	>6*ULN
Gamma-glutamyl-transferase	U/L	(ULN, 2.5*ULN]	(2.5*ULN, 5*ULN]	(5*ULN, 20*ULN]	>20*ULN
Glucose high (hyperglycemia)	mmol/L	(ULN, 8.9]	(8.9, 13.9]	(13.9, 27.8]; hospitalization indicated	>27.8; life threatening consequences
Glucose low (hypoglycemia)	mmol/L	[3.0, LLN)	[2.2, 3.0)	[1.7, 2.2)	[0, 1.7); life threatening consequences; seizures

Lab Test	Unit	Grade 1	Grade 2	Grade 3	Grade 4
Magnesium low (hypomagnesemia)	mmol/L	[0.5, LLN)	[0.4, 0.5)	[0.3, 0.4)	<0.3; life-threatening consequences
Magnesium high (hypermagnesemia)	mmol/L	(ULN, 1.23]	undefined	(1.23, 3.3]	>3.3; life-threatening consequences
Phosphates (hypophosphatemia)	mmol/L	[0.8, LLN)	[0.6, 0.8)	[0.3, 0.6)	[0, 0.3); life threatening consequences; seizures
Potassium high (hyperkalemia)	mmol/L	(ULN, 5.5]	(5.5, 6]	(6, 7]; hospitalization indicated	>7; life-threatening consequences
Potassium low (hypokalemia)	mmol/L	[3, LLN)	[3, LLN); symptomatic; intervention indicated	[2.5, 3); hospitalization indicated	[0, 2.5); life-threatening consequences
Sodium high (hypernatremia)	mmol/L	(ULN, 150]	(150, 155]	(155, 160]; hospitalization indicated	>160; life-threatening consequences
Sodium low (hyponatremia)	mmol/L	[130, LLN)	undefined	[120, 130)	[0, 120); life-threatening consequences

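### If ALT/AST and bilirubin elevations both occur, no planned SAP table counts subjects with ALT/AST ≥3×ULN and total bilirubin >2×ULN together, although the listings would allow a manual count

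*SAP*

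**What the plan says.** SAP 6.6.4 builds its laboratory summaries test by test. "For each laboratory test, Baseline and worst (maximum) CTCAE grade post-Baseline will be identified for each subject", and "Subjects will be characterized only once for a given assay, based on the worst severity grade observed during a period of interest". It adds shift tables from baseline to worst grade, and value and change summaries by visit for Baseline to C2D1 and EOT. These also take one parameter at a time. Listings and summaries of Grade ≥3 abnormalities are optional in the SAP. The SAP does not mention Hy's Law or any output that combines liver tests.

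SAP Appendix 1 (11.1) sets the ALT and AST Grade 2 band at "3.0*ULN, 5.0*ULN" (lower limit excluded, upper limit included). Bilirubin Grade 2 runs from above 1.5 to 3×ULN.

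Protocol 10.4.7 describes a joint event: "a finding of ALT elevation, usually substantial, seen concurrently with bilirubin > 2×ULN". Its numbered components are ALT or AST of 3×ULN or more, total bilirubin above 2×ULN in the same subjects without initial cholestasis, and no other explanation. On the last it says: "It is critical to rule out other causes of injury (e.g., other drugs or viral hepatitis".

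The protocol uses this definition twice. Among the monotherapy escalation DLTs (8.4.1) it lists "Liver enzyme and bilirubin abnormalities meeting Hy's Law criteria (See Section 10.4.7". Among the situations in which treatment may be stopped (7.2) it lists "Liver testing abnormalities meeting Hy's Law criteria (See Section 10.4.7". The combination DLT definition (8.4.2) does not name Hy's Law; its non-hematologic criterion is "Grade ≥ 3 toxicities despite adequate treatment (e.g., nausea, vomiting, diarrhea".

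**The concern.** The pattern in protocol 10.4.7 is about two tests in the same subject, and single-test tables do not carry that information. A case with ALT at 4×ULN and bilirubin at 2.5×ULN is Grade 2 on both tests. It would appear as one Grade 2 entry in the ALT table and one in the bilirubin table, with nothing to connect them.

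This matters because the liver is a named target. Protocol 2.3.1 gives cholestasis and hyperbilirubinemia leading to hepatocellular necrosis as a potential hepatic effect of a first-in-human drug. Protocol 2.2 reports cholestasis with hyperbilirubinemia in the 28-day dog study, though not in the 13-week study. If both kinds of elevation occur, the report as planned would give separate grade counts without saying how many subjects had both.

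**Working it through.** The documents state no figure on this point, so there is nothing to reproduce. The check is whether the planned tables determine the joint count.

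**Inputs (SAP Appendix 1, in ×ULN).** ALT/AST: Grade 1 (1, 3], Grade 2 (3, 5], Grade 3 (5, 20]. Bilirubin: Grade 1 (1, 1.5], Grade 2 (1.5, 3], Grade 3 (3, 10]. Protocol 10.4.7 thresholds: ALT or AST ≥3 and total bilirubin >2.

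**Step 1: thresholds against bands.** Bilirubin of 1.6, 2.0, 2.1 and 3.0 is Grade 2 in every case. Grade ≥2 therefore also counts values from above 1.5 to 2, and Grade ≥3 misses values from above 2 to 3. ALT of 3.0 is Grade 1 and 3.01 is Grade 2, so the ALT/AST threshold matches Grade ≥2 except for a value of exactly 3.0.

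**Step 2: same tables, different joint counts.** Assumed values for two subjects, all other results normal:

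| Case | Subject A | Subject B | Joint count |
|---|---|---|---|
| (i) | ALT 4 and bilirubin 2.5, same sample | normal | 1 |
| (ii) | ALT 4 | bilirubin 2.5 | 0 |
| (iii) | ALT 4 and bilirubin 1.8, same sample | normal | 0 |

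All three give one ALT Grade 2, one bilirubin Grade 2 and none at Grade ≥3. The by-visit maximum might separate (iii) from (i) if the sample fell at a summarised visit. It cannot separate (i) from (ii).

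**Step 3: bounds.** Let a of n subjects be Grade ≥2 on ALT/AST and b on bilirubin. The number Grade ≥2 on both lies between max(0, a+b−n) and min(a, b). The number meeting both 10.4.7 thresholds cannot exceed min(a, b), apart from an ALT/AST of exactly 3×ULN. It may be lower than the number Grade ≥2 on both, because some Grade 2 bilirubin values are at or below 2×ULN. With assumed margins:

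- n=45, a=3, b=3: max(0, 3+3−45)=0 to min(3, 3)=3, that is 0% to 3/45=6.7%. Two constructed data sets, each with 42 Grade 0 and 3 Grade 2 on both tests, have joint counts of 3 and 0.
- n=36 (3, 3): 0 to 3. n=40 (5, 4): 0 to 4. n=75 (6, 4): 0 to 4.

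If b=0 the joint count is zero. If a=0 it is zero apart from an ALT/AST of exactly 3×ULN. In those situations the planned tables are enough.

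**Step 4: other planned outputs.**

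- The DLT output is a listing (SAP 6.6.3). It would name a Hy's Law case as such only in Cycle 1 of monotherapy escalation.
- Grade ≥3 TEAE tables would not pick up a case that is Grade 2 on both tests.
- The disposition table (SAP 6.2) shows a case only if the subject stopped treatment and that reason was recorded. Protocol 7.2 says only that treatment may be stopped.
- By-visit summaries leave out visits between C2D1 and EOT and unscheduled samples (SAP 6.6.1). They are in SI units, while the thresholds are multiples of ULN.
- By-subject listings (SAP 6.1) contain the laboratory data and would allow a manual count.

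**The case against.** The strongest reply is that the SAP does what the protocol asked. Protocol 9.4.4.3 has the same per-assay structure and requests no joint liver summary. Hy's Law enters the protocol as a management criterion, not as an endpoint. All analyses are descriptive, cohorts are small, and every result is listed, so a physician reading the listings can find joint cases. The joint count is also hard to interpret: the drug's own expected signal is cholestatic, entry allows ALT/AST up to 5×ULN with liver metastases, and there is no control arm.

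Most of this stands. The gap is in the planned tables, not in the data, and the SAP does not depart from the protocol by leaving the joint count out. A reader might infer that the tests are tabulated only by worst grade; that is wrong, since by-visit values with minimum and maximum are also planned. A reader might also infer that the Monotherapy Expansion primary endpoint is not delivered. The documents do not support that either: treatment-emergent laboratory abnormalities are defined by change in grade, and the SAP reports them that way.

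What does not stand is that the other outputs make the count unnecessary. Apart from the listings, each covers only one study part, only higher grades, or only cases that an investigator reported or acted on. The listings hold the information, but no one is assigned to count from them and no time window is fixed. The confounding is a reason to show ALP, liver metastases and baseline values beside the count.

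**Conclusion.** The point holds as a gap in the planned summaries. When Grade ≥2 elevations occur on both ALT/AST and bilirubin, no planned table counts subjects who meet the biochemical part of protocol 10.4.7, and the grade tables do not isolate bilirubin above 2×ULN even alone. The conclusion rests on the Appendix 1 bands and on the outputs that the SAP names. Its practical size is unknown, because the documents give no liver-test rates; the counts in the working are assumed and show only that the tables do not determine the answer.

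Two stronger readings should be avoided. Hy's Law cases would not be lost, since the listings retain the values. Nor would a joint count diagnose Hy's Law, since 10.4.7 also requires ruling out obstruction and other causes.

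A separate, minor point: protocol 9.4.4.3 commits to the Grade ≥3 laboratory listings and summaries, the SAP makes them optional, and SAP Section 8 does not record the change. That output is also per test, so it lends no support to the joint-count point.

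**What to change.** Add to SAP 6.6.4, by study part, dose and therapy, the number and percentage of subjects with:

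- post-baseline ALT or AST ≥3×ULN;
- post-baseline total bilirubin >2×ULN;
- both within a stated window, for example in the same sample and, separately, within 28 days (one cycle), each shown with and without ALP elevation.

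Add a by-subject listing of joint cases, labelled as a screening flag pending clinical adjudication. It should flag liver metastases and baseline elevation, because protocol 5.1 allows raised ALT/AST with liver metastases and limits total or conjugated bilirubin, so total bilirubin may already be high at entry. A plot of peak ALT/AST against peak bilirubin is optional.

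The cost is one table, one listing and clinical review of any flagged case, with no new sampling. Coverage is not systematic after the 18 May 2022 cut-off, when only limited data were collected (SAP Section 8), and the output should say so.

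Separately, make the Grade ≥3 laboratory output firm again, as in protocol 9.4.4.3, or list the change in SAP Section 8.
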